# II. OBJECTIVES

This protocol describes the PRISM program's efforts to establish the methodological framework for studying pregnancy outcomes following exposure to vaccination during pregnancy. The results of this infrastructure building and methods development activity will be used to determine the feasibility of pregnancy surveillance within Mini-Sentinel's PRISM program and to evaluate the novel methods required to conduct such surveillance. The overarching goal of this protocol is to optimize algorithms for using claims and birth certificate data in studies of pregnancy outcomes. In addition, we will examine the feasibility of conducting a case-time-control design for examining risk of SAB following exposure to TIV using risk intervals defined by gestational age at vaccination and by the time elapsed since vaccination.

#### A. PRIMARY OBJECTIVES

- 1. To examine the positive predictive value of computerized CPT or ICD9 codes for SAB through medical record review for all cases combined and by maternal age and by code
- 2. To examine the accuracy of gestational age data in claims and in birth certificate data for the purposes of identifying pregnancy start among live delivery controls, who will be matched to chart-confirmed SAB cases

3. To examine the accuracy of potential confounders in claims data for the purposes of matching SAB cases and live delivery controls

#### **B. PILOT OBJECTIVES**

Using a case-time-control design, to examine risk of SAB following TIV using the following risk intervals:

- 4. In the 1-28 days post-TIV
- 5. After TIV received between -4 and 4 weeks gestation, 2 and 6 weeks gestation, or 6 and 11 weeks gestation

To explore potential periods for increased risk of SAB without defining the risk interval a priori:

- 6. Within a specific time interval defined by number of days post-TIV
- 7. After TIV received during a specific gestational period
- 8. Within a specific time interval defined by number of days post-TIV and gestational period at vaccination

### **III. STUDY DESIGN**

#### A. OVERVIEW OF CASE-TIME-CONTROL DESIGN

In this protocol, our main objective is to optimize algorithms for using claims and birth certificate data for studies of pregnancy outcomes. As proof-of-concept, we will also determine the feasibility of implementing a case-time-control design to examine whether risk of SAB is elevated within 1-28 days post-TIV or whether the risk is increased after TIV received between -4 to 4 weeks gestation, between 2 to 6 weeks gestation, or between 6 to 11 weeks gestation. We will match cases and controls (at least two controls per case, up to a maximum of 6) on Data Partner, maternal age, and pregnancy start date (i.e.., date of last menstrual period (LMP), pregnancy start based on ultrasound dating, or pregnancy start based on assisted reproductive technology; see methods for determination). Matching on pregnancy start in cases and controls will address temporal patterns in vaccination by seasonality and gestational age. If feasible, we will also attempt to match cases and controls on comorbidities, infections, and other potential confounders, which will maximize the comparability between cases and controls with respect to underlying time trends in exposure.

The case-time-control design is a variant of a case-cross-over study (CCO). The CCO study and its variants are especially well-suited to measuring transient effects of exposures on immediate risk of illnesses with abrupt onset. In a CCO study, in individuals who have experienced the outcome of interest, a comparison is made between the odds of exposure in a predefined risk interval to that in a self-matched comparison interval. In addition to using cases as the CCO study does, the case-time-control design also uses an external group of controls sampled from the same population that produced the cases to adjust for time trends in exposure (e.g., seasonality or gestational age at vaccination). As in the cases, in the controls, the odds of exposure is compared between the predefined risk and self-matched control interval to estimate the exposure trend bias; the odds ratio in cases is divided by the odds ratio in controls to produce an effect estimate for the association between exposure and outcome while adjusting for time trends in exposure.

In the pilot objectives, we will utilize a case-time-control design to examine whether risk of SAB is elevated in pre-specified periods by number of days between TIV receipt and SAB event and by gestational age at receipt of TIV. For defining exposure by number of days prior to SAB event, we propose to use the risk interval of 1-28 days prior to SAB. Previous studies suggest that antibody secreting cells increase in peripheral blood within days of vaccination with peak antibody titers occurring 2-3 weeks following administration of seasonal influenza vaccine in healthy non-pregnant individuals. Furthermore, inflammatory immune responses in pregnant women following TIV, as measured by C-reactive protein and tumor necrosis factor-alpha, have been shown to peak at 2 days post vaccination and return to baseline levels within one week post-vaccination. From a biologic plausibility standpoint, one may hypothesize that the period of risk corresponds with this approximately 4-week long period of heightened immunologic activity if immune mediated reactions are the cause of potential adverse events.

When defining exposure by gestational age, we will examine risk intervals of -4 through 4 weeks gestation, 2 through 6 weeks gestation, and 6 through 11 weeks gestation. The -4 through 4 weeks gestation risk interval was selected because immune-mediated processes resulting from vaccination in the weeks surrounding conception and the early pregnancy period may lead to increased risk of SAB. Previously, Wacholder et al. found a small increase in risk of SAB following receipt of bivalent vaccine against human papillomavirus types 16 and 18 (Cervarix®, manufactured by GlaxoSmithKline) in the subgroup of pregnancies conceived within 90 days prior to vaccination, though the authors concluded that this result was consistent with statistical noise. Furthermore, in the VSD, a non-statistically significant increase in risk of SAB was found among women receiving TIV in the 14 days preceding conception (OR 2.3, 95% Cl 0.9, 6.3), compared to women not receiving TIV. For the present protocol, we selected an additional risk interval of 2 to 6 weeks gestation to reflect the period of early pregnancy, based on the rationale that inflammatory markers, systemic, and local reactions could potentially manifest and end within a shorter period following vaccination. We also selected an additional risk interval of 6 to 11 weeks gestation to correspond to the period of the highest incidence of SAB, which could reflect an increased period of susceptibility.

For each of the pilot case-time-control analyses, the control interval will be defined as vaccination outside each of the risk intervals. One advantage of the case-time-control design is that it adjusts for between-person confounders that do not vary over time. However, a disadvantage is that the design will not completely adjust for time trends in exposure if controls have different time trends in exposure than cases. This might occur if women at greater risk of SAB are more likely to be vaccinated at an earlier or later gestational age than those at lower risk. Furthermore, a major disadvantage of this approach is that the risk interval must be defined a priori.

#### B. OVERVIEW OF TEMPORAL SCAN FOR IDENTIFICATION OF RISK INTERVALS

In vaccine safety studies, the risk interval should correspond with the true period of increased risk following vaccination. If the risk interval contains days in which there is no true increase in risk, the magnitude of an increased risk could be underestimated or completely missed. Conversely, using too short of a risk interval could lead to a loss of power for relative incidence estimates. The specific choice of risk interval in vaccine studies should be informed by biologic plausibility to avoid bias and loss of power. However, because the pathophysiology of SAB is largely unknown, the case-time-control design may be susceptible to bias due to incorrectly specifying the risk interval.

**PRISM Surveillance Protocol** 

To address the limitation of pre-defining the risk interval in the case-time-control approach, we propose to explore additional techniques that do not define the specific risk intervals a priori. Specifically, we propose to use temporal scan methodology to identify potential risk periods of interest in relation to vaccine receipt. The temporal scan approach has been used in prior studies in order to more precisely define the risk interval in signal refinement within a longer post-vaccination observation period. In this protocol, a temporal scan approach will be used to detect and evaluate temporal clusters of vaccination among women with SAB who have received TIV in the period of interest, adjusted for underlying temporal patterns in vaccination by gestational age and calendar week. Because the pathophysiology of SAB is not well understood, we will examine for clusters by timing of TIV receipt in several ways: (1) number of days prior to SAB event, (2) gestational age at receipt of TIV, and (3) a combination of number of days prior to SAB event and gestational age at receipt of TIV. We will use women who have had live deliveries as controls to adjust for temporal trends in TIV receipt by gestational age and calendar time.

### C. DATA SOURCES

The PRISM data sources currently consist of claims-based and administrative data from Data Partners and immunization registry data from Immunization Information Systems (IIs) in Departments of Health in 7 states and New York City. Claims-based and administrative data from Data Partners include data on demographics, diagnoses, procedures, and pharmacy dispensings. Under the protocol of a separate activity entitled "PRISM Influenza Vaccines and Birth Outcomes", methods are being developed to link maternal and infant Data Partner records and to link maternal Data Partner records and birth certificate data from Vital Events Registries in select cities and states. For the current protocol, infant claims-based data and birth certificate data will be used, if available, in the process of matching controls (i.e. deliveries) to cases (i.e., SABs) on pregnancy start date since these data sources provide more precise estimates of gestational age than maternal claims-based counterparts. Electronic data (claims-based, administrative, and birth certificate data, where available) will be used for identifying cases and controls. However, only chart-confirmed cases and controls, as well as chart-confirmed gestational age and date of SAB will be used in the final analysis.

#### D. STUDY POPULATION

The participating Data Partners in this protocol are Aetna and HealthCore. The dates of data availability differ by Data Partner (Table 1). The study population will consist of females ages 18 through 34 years who received TIV in the 4 weeks prior to or during pregnancy, and whose pregnancies have ended in an SAB (cases) or live delivery (controls). Women whose pregnancies have ended in a therapeutic abortion, ectopic or molar pregnancy, or stillbirth will not be used as controls since we will not be able to accurately assess gestational age using claims-based data. The study population will be further restricted to women with continuous enrollment from 90 days prior to pregnancy start through the SAB date in cases or index date in controls. Though we do not anticipate this to occur frequently, cases and controls who receive an additional influenza vaccine in the 90 days prior to the start of the study period of interest (i.e., -4 weeks gestation) will be excluded.

Data Partner	Date Data Available in Mini- Sentinel Common Data Model	Requirements for Data Used in Protocol 
Data Partner A	1/1/2008 through 10/31/2012	Vaccinations occurring in 2008-09 and 2010-11 influenza seasons
Data Partner B	1/1/2004 through 11/30/2011	Vaccinations occurring in 2008-09 and 2010-11 influenza seasons

Table 1: Dates of Data Availability by Data Partner

Influenza season defined as September 1 through April 30 of the following year. 2009-10 influenza season not included due to the availability of H1N1 influenza vaccine in the same season.

#### E. OVERVIEW OF SELECTION OF CASES AND CONTROLS

Vaccinated cases (SAB) and controls (deliveries) for this protocol will be selected in a 4-phase process (Figure 1), with a targeted final sample of 100 cases, with each case matched to at least 1 control in the final analysis. In phase 1, 140 potential cases will be initially identified in claims-based and administrative data. Also in phase 1, the initial step of identifying deliveries and estimating their pregnancy start will occur using claims-based and administrative data. If more than 140 potential cases are identified in electronic data, we will randomly sample 70 cases from each Data Partner. In phase 2, chart review will be conducted on potential cases to confirm SAB, date of SAB, and obtain pregnancy start date; potential cases will only be retained if vaccination occurred during the gestational period of interest (-4 weeks gestation to SAB event date). In phase 3, for each chart-confirmed case, we will identify 2 potential controls with the same age, pregnancy start, and vaccination between -6 weeks gestation and 2 weeks past the case's gestational age at SAB, based upon electronic data. We will randomly sample a minimum of 2 controls for each case. In the final phase, we will chart review potential controls to confirm pregnancy start, vaccination, and gestational age at vaccination.

Mini-Sentinel

Figure 1: Case and control selection for PRISM Influenza Vaccines and Pregnancy Outcomes Assessment

# F. IDENTIFYING POTENTIAL CASES AND CONTROLS IN CLAIMS-BASED AND ADMINISTRATIVE DATA (PHASE 1)

#### 1. Cases

The inclusion criteria for cases and controls are summarized in Appendix 1. Using claims and administrative data, women who have experienced a SAB will be initially identified using the codes in Appendix 2 occurring in the inpatient, emergency department, or ambulatory care setting. To avoid including follow-up visits, a 98-day (i.e., 14 week) washout period will be used to identify incident SAB events. If there are multiple incident SAB events for a given patient, we will select the first chronological event in the study period. Though the average gestational length of pregnancies ending in miscarriage is shorter (i.e., 10 weeks), we chose the 14-week washout period to enhance the specificity for detecting incident SAB events. Initially, inclusion based on period of enrollment will be conducted through the use of administrative and claims-based data; women whose pregnancies have ended in a SAB will only be considered a potential case if based on claims-based and administrative data, they are enrolled continuously for the 244 days prior to their medical encounter for SAB. The 244-day pre-SAB enrollment criterion for potential cases incorporates a 90-day period prior to pregnancy start, 140-day period for the maximum gestational length for a pregnancy ending in SAB, and a 14-day period to allow for delays in seeking medical attention for SAB.

We will also initially require, based on electronic data, potential cases to have received TIV within the 1-182 days prior to the SAB code. This 182-day (i.e., 26 week) period was selected to enhance our ability to detect vaccinations during the gestational period of interest (-4 weeks gestation through SAB event date) and incorporates a 20-week period corresponding to the latest gestational age at which a SAB may occur, a 4-week period corresponding to the pre-gestational period of interest, and a 2-week period to allow for delays in seeking medical care for miscarriage. After the SAB event date is confirmed, we will ensure that cases are enrolled for a minimum of 90 days prior to pregnancy start through the SAB event date and will only retain cases with TIV in the period of interest (-4 weeks gestation through SAB event date). While we will use claims data to initially identify potential cases, we will limit our analysis to chartconfirmed cases and will use medical record data to identify the start of pregnancy and the date of SAB to reduce misclassification of timing of exposure with respect to gestational age and days in relation to SAB. The process of medical record review will be described later in the protocol.

#### 2. Controls

We will identify live deliveries in claims-based and administrative data using codes in Appendix 3. To avoid including post-partum care visits, we will use a washout period of 270 days to define an incident delivery. For women who have both a SAB and live delivery during the study period, the SAB will be retained, while the live delivery will be discarded; this will be done to retain the SAB in instances where multiple pregnancies result in one or more miscarriages, and the remaining fetus(es) results in a live delivery. Initially, inclusion based on period of enrollment will be conducted with administrative and claims-based data; women whose pregnancies have ended in a delivery will only be considered for inclusion as a potential control if based on claims-based and administrative data, they are enrolled continuously for the 360 days prior to delivery hospitalization. The 360-day pre-delivery enrollment criterion for potential controls incorporates a 90-day period prior to pregnancy start and a 270-day period, the average length of term pregnancy. After chart review is conducted, we will ensure that controls are enrolled for a minimum of 90 days prior to pregnancy start through the index event date in

**PRISM Surveillance Protocol** 

the matched case and will only retain controls with TIV in the period of interest (-4 weeks gestation through index event in the matched case). While we will use claims data to initially identify potential controls and estimate gestational age, we will use medical record data to confirm the gestational age to reduce misclassification of timing of exposure.

# G. CHART REVIEW OF POTENTIAL CASES IDENTIFIED IN CLAIMS-BASED AND ADMINISTRATIVE DATA (PHASE 2)

Once potential SAB cases are identified using computerized data, we will conduct medical record review to confirm the SAB event and estimate the dates of SAB and pregnancy start, which will be used to calculate gestational age at vaccination and timing of vaccination (in days) in relation to SAB. We will exclude naturally conceived pregnancies ending in a miscarriage (i.e., SAB cases) that do not have LMP since we will be unable to estimate gestational age at vaccination. Following chart review, we will only retain those potential cases that have TIV occurring in the gestational period of interest (-4 weeks gestation through the date of SAB). Details on the types of data needed to validate the date of the SAB event and pregnancy start will be described later in the protocol.

#### H. MATCHING POTENTIAL CONTROLS TO CHART-CONFIRMED CASES (PHASE 3)

After chart review of potential cases, we will identify 1 or more potential controls (up to a maximum of 6 controls) for every case to pursue medical charts. Controls will be matched to cases on Data Partner, age, and pregnancy start (+/- 14 days), with pregnancy start estimated initially in electronic data and chart-confirmed at a later stage. Matching on pregnancy start will address temporal trends in exposure by gestational age and calendar time by maximizing the comparability between cases and controls with respect to the gestational and calendar periods covered by the risk and control intervals. Furthermore, matching on Data Partner and, maternal age will address confounding, which might occur if these factors are associated both with SAB and with timing of vaccination. If sufficient controls are available, we will also attempt to match on other important confounding factors, including comorbidities and infections, further described later in the protocol. Conditional logistic regression will be used to account for the matching and to allow for a different underlying time trend in exposure for each case:control set, which addresses the possibility of effect modification of the exposure-period association by confounders matched upon.

The matching criteria are described in more details as follows. We will match cases to controls on pregnancy start, Data Partner, and maternal age within +/-18 months. Among potential controls, we will initially estimate pregnancy start date based on an algorithm that utilizes electronic data and that is further described in the PRISM Influenza Vaccines and Birth Outcomes Protocol. Because birth certificate data and infant claims-based codes for gestational age provide more precise estimates of gestational age than their maternal claims-based counterparts, we will link potential controls identified in Data Partner records to infant Data Partner records and/or birth certificate data. We will use claims-based codes for gestational age for infants born preterm, post-term, or after a prolonged gestation (Appendix 4). If claims-based codes for gestational age for gestational age for infants age for infants in Appendix 4 are not evident, we will assume a gestational length of 270 days.

If there are sufficient control numbers, we will consider matching controls to cases on diagnoses of diabetes, obesity, asthma, and multiparity based on CPT and ICD9-coded data. Finally, where information on particular time-varying confounders is available in claims-based data, we will attempt to match cases and controls on such factors if sufficient controls exist. We will attempt to match cases and controls on the presence of urinary tract infections, respiratory infections, gastrointestinal infections, sexually transmitted infections, and medically attended fever within a 1-28 day period prior to SAB/index date, identified using ICD9-coded data (Appendix 5). Finally, we will collect information from the medical record on factors not matched upon in the design phase, such as smoking, alcohol, and substance abuse, and adjust for them in regression models if feasible.

Multiparity will be identified using codes listed in Appendix 5. The algorithms for identifying obesity and diabetes are described in the PRISM Influenza Vaccines and Birth Outcomes Protocol. Asthma will be identified using an algorithm validated and developed by the Medication Exposure in Pregnancy Risk Evaluation Program (MEPREP), an FDA-sponsored collaboration between 11 health plans. To be considered asthmatic, a woman must have one of the following during the 90 days prior to pregnancy through end of pregnancy: (1)>=2 outpatient visits at least 30 days apart with ICD9 diagnosis code 493\*, (2) >=1 inpatient visit with ICD9 diagnosis code 493\*, or (3) >=1 outpatient visit with ICD9 diagnosis code 493\* and >=1 dispensing of an asthma medication (short- or long-acting beta-agonist, inhaled corticosteroid, leukotriene receptor antagonist, mast cell stabilizer, methylxanthine). This algorithm was shown to have a positive-predictive value of 95% in MEPREP.

Among potential controls meeting matching and enrollment criteria, TIV identified in claims or IIS data must be received between -6 weeks gestation and 2 weeks past the case's gestational age at SAB, with gestational age estimates from birth certificate or infant-claims based estimates. A 2-week margin before and after the gestational period of interest will be initially incorporated to allow for misclassification of gestational age in live delivery controls due to use of claims and birth certificate data for gestational age estimates.

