# I. BACKGROUND AND PUBLIC HEALTH IMPLICATIONS

#### A. SPONTANEOUS ABORTION

Spontaneous abortion (SAB) is one of the most common complications of pregnancy, resulting in fetal loss prior to 20 weeks of gestational age. Between 12% to 15% of clinically recognized pregnancies result in a SAB, with the vast majority occurring prior to 12 weeks gestation. When including clinically unrecognized pregnancies, the pregnancy loss rate is substantially higher, with one carefully conducted study including such pregnancies finding a loss rate of approximately 30% following implantation.

Chromosomal anomalies are implicated in approximately half of all SABs, with a higher incidence of abnormal fetal karyotype at earlier gestational ages; an additional unknown proportion of SABs is due to genetic abnormalities undetected by standard karyotype analysis. The etiology of SAB in apparently healthy women with chromosomally and structurally normal fetuses is unknown. One of the most important risk factors is age, with rates increasing with maternal age (9% at age 22, 20% at age 35, 55% at age 42, and 84% at age 48 years and above). Other factors associated with SAB include smoking, alcohol, asthma, parity, prior history of SAB, diabetes, febrile illness, and obesity.

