In Pilot Objectives 4-5, we will implement the case-time-control design and analyze the resulting data. For Pilot Objective 4, we will define the risk interval as receipt of TIV within 1-28 days prior to SAB, while the control interval will be defined as receipt of TIV outside of the risk interval (i.e., between -4 weeks gestation and 29 days prior to SAB, Figure 2). Although we will strive for an exact match by pregnancy start, it is plausible that we will not identify enough controls to match to cases. If an exact pregnancy start match is not possible, we will assign an index date in controls that corresponds to the gestational age at SAB in the case. Of note, cases and controls will only be informative if vaccinated in either the risk or the control interval. In exploratory analysis, we will stratify the analysis for this objective by gestational age at SAB (less than 12 weeks gestation vs. 12 or more weeks gestation) since the etiology of SAB differs by gestational age at occurrence. In addition, because the underlying causes of SAB may differ by whether a heartbeat is detected prior to the miscarriage, we will consider stratifying by this factor, depending on whether we have sufficient case numbers. If we have sufficient case numbers, we will also consider excluding cases that have a threatened abortion identified prior to vaccination.

**Figure 2:** Example case and control for case-time-control design with the risk interval defined as 1-28 days before SAB, and the control interval design defined as -4 weeks gestation through 29 days before SAB. Follow-up time after the SAB and index dates will be censored.

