risk of miscarriages early during pregnancy. While we will mitigate the potential for confounding by indication by only including vaccinated individuals, the case-time-control study and temporal scans may be biased if the temporal trend of exposure in controls does not represent that of cases. This may be true if a third factor is associated both with the timing of vaccination and case vs. control status (i.e., risk of SAB). We will match on maternal age, infections, and pregnancy start to minimize confounding by gestational age or calendar time and will attempt to match on diabetes, obesity, asthma, and parity if there are adequate numbers of potential controls. However, it is not possible to match on other factors not captured fully in claims-based data, including smoking, alcohol, substance abuse, environmental toxins, and prior history of SAB. While we will collect information on a number of these risk factors in medical records and conduct descriptive analyses, they are not always systematically recorded in the medical record. The control population in this study is limited to mothers that have been linked to birth certificate data and/or infant Data Partner records. If these women differ with respect to comorbidities or healthcare utilization from the general population of live deliveries, our selected group of controls may not be representative of the temporal trend in exposure in cases. We will compare the characteristics of live delivery controls by study inclusion status and consider matching to cases on comorbidities as feasible. In addition, differential misclassification of gestational age at vaccination may occur if dating accuracy differs by case status. Finally, while the temporal scan techniques overcome the limitation of pre-defining the period of risk, they may produce overestimates of relative risk if the study is underpowered. Furthermore, no confidence intervals are produced with this technique. As such, the temporal scan should be considered exploratory.

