Appendix 4: ICD9 codes used to estimate gestational age at delivery

## Appendix 5: ICD9 codes used for identifying confounders

Confounder	Code	Description
Fever	780.6	FEVER & OTH PHYSIOLOGIC DISTURBANCES TEMP REG
Fever	780.60	FEVER UNSPECIFIED
Fever	780.61	FEVER PRESENTING CONDITIONS CLASSIFIED ELSEWHERE
Fever	780.62	POSTPROCEDURAL FEVER
Fever	780.63	POSTVACCINATION FEVER
Gastrointestinal infection	001	CHOLERA
Gastrointestinal infection	001.0	CHOLERA DUE TO VIBRIO CHOLERAE
Gastrointestinal infection	001.1	CHOLERA DUE TO VIBRIO CHOLERAE EL TOR
Gastrointestinal infection	001.9	UNSPECIFIED CHOLERA
Gastrointestinal infection	002.0	TYPHOID FEVER
Gastrointestinal infection	002.1	PARATYPHOID FEVER A
Gastrointestinal infection	002.2	PARATYPHOID FEVER B
Gastrointestinal infection	002.3	PARATYPHOID FEVER C
Gastrointestinal infection	002.9	UNSPECIFIED PARATYPHOID FEVER
Gastrointestinal infection	003.0	SALMONELLA GASTROENTERITIS
Gastrointestinal infection	003.8	OTHER SPECIFIED SALMONELLA INFECTIONS
Gastrointestinal infection	004.0	SHIGELLA DYSENTERIAE
Gastrointestinal infection	004.1	SHIGELLA FLEXNERI
Gastrointestinal infection	004.2	SHIGELLA BOYDII
Gastrointestinal infection	004.3	SHIGELLA SONNEI
Gastrointestinal infection	004.8	OTHER SPECIFIED SHIGELLA INFECTIONS
Gastrointestinal infection	004.9	UNSPECIFIED SHIGELLOSIS
Gastrointestinal infection	005	OTHER FOOD POISONING
Gastrointestinal infection	005.0	STAPHYLOCOCCAL FOOD POISONING
Gastrointestinal infection	005.1	BOTULISM FOOD POISONING
Gastrointestinal infection	005.2	FOOD POISONING DUE TO CLOSTRIDIUM PERFRINGENS
Gastrointestinal infection	005.3	FOOD POISONING DUE TO OTHER CLOSTRIDIA
Gastrointestinal infection	005.4	FOOD POISONING DUE TO VIBRIO PARAHAEMOLYTICUS

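### If fever is matched or adjusted for as written, fever caused by the vaccine is counted as a confounder, which pulls the Pilot Objective 4 odds ratio toward 1 for any effect that runs through fever

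*Protocol*

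**What the plan says.** Section III.H treats infections and fever as time-varying confounders. For these it says "we will attempt to match cases and controls on such factors if sufficient controls exist", and the list of factors ends "and medically attended fever within a 1-28 day period prior to SAB/index date, identified using ICD9-coded data (Appendix 5". The Appendix 5 fever codes include 780.63, "POSTVACCINATION FEVER".

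For Pilot Objective 4, Section III.K says "we will define the risk interval as receipt of TIV within 1-28 days prior to SAB". The control interval is the remaining time back to -4 weeks gestation. Section IV.B adds that time-varying confounders not matched on will be adjusted for in the regression where applicable.

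Two other places bear on fever. Section I.A states: "Other factors associated with SAB include smoking, alcohol, asthma, parity, prior history of SAB, diabetes, febrile illness, and obesity". The rationale in Section III.A rests partly on "inflammatory immune responses in pregnant women following TIV", and for the 2 to 6 week interval on the idea that "inflammatory markers, systemic, and local reactions could potentially manifest and end within a shorter period following vaccination".

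The Limitations (V.B) are firmer about infections than Section III.H: "We will match on maternal age, infections, and pregnancy start to minimize confounding by gestational age or calendar time". Fever is not named there.

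**The concern.** A matching factor should be something that could influence both the timing of vaccination and the risk of spontaneous abortion (SAB). Fever that follows vaccination cannot have influenced when the vaccine was given. If the vaccine caused the fever, and fever raises SAB risk, then fever is a step between exposure and outcome.

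The controls in a case-time-control study supply the background pattern of vaccination timing. A control chosen because she also had recent fever is more likely to have been vaccinated recently, wherever the vaccine causes fever. The comparison then no longer contains the part of the effect that passes through fever. In a safety study this error is in the less protective direction. Putting the same fever variable into the regression has the same consequence, so the fallback in Section IV.B does not avoid it.

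**Working it through.** **Timing.** Count days back from the SAB or index date. The fever window is days 1-28, and so is the Objective 4 risk interval.

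- A woman vaccinated on day 20 has days 21-28 of the fever window before vaccination and days 1-19 after it.
- A woman vaccinated on day 29 or earlier has the whole fever window after vaccination. Section III.A says the measured inflammatory markers return to baseline within a week, so little of her fever in that window is likely to be vaccine-caused.
- Vaccine-caused fever in the window therefore points mainly to women vaccinated in the risk interval. Code 780.63, by its own label, follows a vaccination.

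By contrast, Section III.K ties another time-varying factor, threatened abortion, to the time before vaccination.

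**Plan's own figures.** The documents give no fever rate and no expected effect through fever. The only power figure (about 80% for a relative risk of 2.4 in Section V.B) concerns the 2 to 6 week interval. The argument here does not use it.

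**Size under assumptions.** Let f0 and f1 be the risks of attended fever without and with vaccination in the risk interval, and RF the ratio of SAB risk with fever to that without. Then

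total ratio = direct ratio × [1 + f1(RF − 1)] / [1 + f0(RF − 1)].

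Exact matching on fever leaves only the direct ratio. With f0 = 3% and a direct ratio of 1 (all inputs assumed):

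| Extra attended fever (f1 − f0) | RF | Without fever matching | With fever matching |
|---|---|---|---|
| 1% | 2 | 1.04/1.03 = 1.01 | 1.00 |
| 2% | 2 | 1.05/1.03 = 1.02 | 1.00 |
| 10% | 2 | 1.13/1.03 = 1.10 | 1.00 |
| 10% | 3 | 1.26/1.06 = 1.19 | 1.00 |
| 20% | 3 | 1.46/1.06 = 1.38 | 1.00 |

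**Check by simulation.** One-to-one matching was simulated in 4 million women per setting, with a 35% chance of risk-interval vaccination, 3% background fever and 2% baseline SAB risk (all assumed). Pair odds ratios without and with fever matching were:

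- 2% extra fever, RF 2, direct ratio 1: 1.03 and 1.01
- 10% extra fever, RF 3, direct ratio 1: 1.21 and 1.01
- 20% extra fever, RF 3, direct ratio 1: 1.39 and 0.99
- 10% extra fever, RF 3, direct ratio 2: 2.46 and 2.07

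The part that runs through fever is removed and the direct part stays. In the last setting the formula gives 2 × 1.19 = 2.38. The simulated values are odds ratios, which lie somewhat above risk ratios when the outcome is not very rare.

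**The case against.** The strongest reply is that little of this may ever happen. Matching beyond Data Partner, age and pregnancy start is an attempt that depends on control numbers (III.A, III.H, III.K, Appendix 1). The only unconditional sentence, in V.B, concerns infections and not fever. The affected analyses are pilot analyses with admittedly limited power. Section III.O already collects febrile illness from charts, mainly for description. All of this stands. It makes the point conditional but does not remove it, because the definition is wrong whenever it is used, whether in matching or in the model.

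A reader might infer that matching on the listed infections is equally at fault because they share the window. The documents do not support that. Nothing in them suggests that an inactivated vaccine causes urinary, gastrointestinal, respiratory or sexually transmitted infection, and being dated after vaccination does not make a variable a consequence of it. Such infections can be genuine confounders.

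A reader might also infer that the design erases the vaccine effect, or that every fever-matched pair drops out. Neither follows. A control with fever can still have been vaccinated in the control interval, so discordant pairs remain, and a direct effect is preserved. Fever as a step on the path is itself an inference from the protocol's mention of inflammatory and systemic reactions. Section III.A does not name fever.

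**Conclusion.** The point holds in a limited form. As written, the plan allows matching or adjustment on a consequence of vaccination, in the same 28 days that define exposure for Pilot Objective 4. The direction is toward 1 for whatever part of an effect runs through fever. This assumes that the vaccine raises attended fever and that fever raises SAB risk.

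The size cannot be determined from the documents. With 1-2% extra attended fever and a doubled SAB risk it is only about 1-2% of the ratio. It becomes material only under much higher assumed fever rates, such as 10-20% extra with a tripled risk.

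The windows coincide only for Objective 4. Objective 5 and the temporal scans reuse the same matched sets and are affected in part. Primary Objectives 1-3 are not biased by this, although Objective 3 would validate the fever definition as it now stands.

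**What to change.** Three changes:

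1. Delete 780.63 from the Appendix 5 matching list.
2. In III.H and IV.B, count fever as a matching or adjustment factor only when it is dated before vaccination.
3. Report fever between vaccination and the SAB or index date descriptively, by case status.

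The second change needs its own look-back for fever, of equal length in cases and controls and ending the day before vaccination. Adding the condition to the present window would not work: a woman vaccinated in the control interval would have no eligible day, and fever status would then reveal exposure. A 28-day look-back, for example, fits the data already required. The earliest eligible vaccination is 28 days before pregnancy start, so the window reaches back 28 + 28 = 56 days, inside the 90 days of required enrolment.

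Matching on infections can stay as planned.

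The change costs a few lines of text and one code. Fewer fever events will be available for matching, and some control for unrelated febrile illness after vaccination is given up. Fever will also be measured at different gestational ages within a pair. The retained infection codes cover part of that loss.
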